10.0 Quality Control and Quality Assurance

The PI will ensure adherence with the protocol and for accuracy in relation to source documents. Meetings with UIC students will be held regularly to ensure research study aims are being adhered. While Centro Comunitario Juan Diego and The Resurrection Project will be helping with recruitment, they will not be involved in administrative components of the research process, such as eligibility screening and obtaining consent. Further they will not have any access to data from this project.

The PI is responsible for the evaluation of data quality and how frequently this will be done.

11.0 Data and Safety Monitoring

Oversight of the progress and safety of the trial will be provided by the PI. Adverse events are not anticipated, but any occurring will be documented and reported according to UIC IRB policies and procedures. Study progress summary will be communicated to the IRB at the time of continuing review.

All participant information, including intervention development focus group audio-recordings and transcripts as well as the survey questionnaires, will be protected for confidentiality to the fullest extent possible. [name] will have a key to the office where data will be stored and will oversee all data management. The data will be stored on the UIC/SPH R drive (R = Research) and the assigned folder will be locked down the folder and restricted access only for the PI and UIC study staff. The School of Public health's secure network server will have Active Directory controlled access and BitLocker encryption.

All individuals who handle the data will be required to sign a form that they agree to handle the data in a confidential matter. Further, [name] will ensure that all investigators involved with the project undergo training through a general information technology security awareness program offered through the SANS Institute (www.sans.org).

With regard to the coded nature of the data, two master files will be created. The first will include identifiable elements, the participant identification code, the dates in which women have been contacted/interacted with staff (e.g., for screening; for scheduling; to participate in intervention sessions; for booster calls), coupon numbers assigned to them, and the number of individuals who have called with the coupon numbers assigned to them. This information will only be kept across the months in which the participant is enrolled in the study. For participants were in Cohort 1 (who completed participation before approved consent addendum), they will be contacted by phone up to 3 times with a script including consent addendum information to be given that information, wherein they can elect to be notified about future studies, if they are interested. If they are not interested, their data will be eliminated from this file. For cohorts 2-15, after the participant completes the final/third survey, her data will be eliminated from this file, if she chooses not to be contacted for future studies. If she chooses to be contacted for future studies, her information will be kept and it will be recorded that she has completed participation, but is willing to be contacted in the future. The file will be password-protected and stored within

a secured folder on The School of Public health's secure network server, which has an Active Directory controlled access and BitLocker encryption. Only UIC-based study staff will have access to this file in terms of the password and the location.

The second file will include the participant identification code and survey data, but will not have identifiable elements attached. This file will be kept in a separate location/folder within The School of Public health's secure network server.

Risk of access to participant computer-stored information will require simultaneous knowledge of data format, file name, password, and computer language. No individuals will be identified in any reports from the study. Confidentiality of participants will be protected in this project, in that their names and contact information will be kept in a separate file that has no connection to the identification codes used in questionnaires or anonymous transcripts. Transcripts, questionnaire and electronic medical record data will be coded and managed as separate files in a protected part of the computer network. Audio-recordings will be recommended in WAVE files. Transcripts will be saved as .pdf files. Personal health identifying (PHI) information will be saved in XML files. De-identified survey questionnaire data will be kept in standard statistical packages, including SPSS, SAS, and Stata. We will regularly make backups of data. No information will be released that could lead to identification of any participating individual. All files will be encrypted/password-protected. We will log dates when the data are handled.

We will have regular study team meetings to discuss data handling issues. Any breaches in confidentiality or privacy will be promptly reported to the UIC IRB for review and action.

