Six months after participation in Session 3, participants will be asked to complete Survey 3, which will take about 20-30 minutes. Survey 3 will be administered or in person at Centro Comunitario Juan Diego or The Resurrection Project sites. The reminder script has been modified to include scheduling calls, including for Survey 3 as well as the focus groups. Survey 3 will collect information related to information related to volunteerism history, social interactions, breast cancer beliefs (cultural beliefs, perceived risks, norms and social interactions concerning breast cancer) and breast cancer screening since Survey 1. For participants were in Cohort 1 (who completed participation before approved consent addendum), they will be contacted by phone up to 3 times with a script including consent addendum information to be given that information, wherein they can elect to be notified about future studies, if they are interested. If they are not interested, their data will be eliminated from this file. For cohorts 2-15, after the participant completes the final/third survey, her data will be eliminated from this file, if she chooses not to be contacted for future studies. If she chooses to be contacted for future studies, her information name and phone number (nothing else) will be kept and it will be recorded that she has completed participation, but is willing to be contacted in the future. Subsequently, each time she is contacted, this file will be updated to include a summary of the call. During each call, UIC staff will query the woman about her interest in being contacted in the future. If she chooses not to be contacted from future studies, her name and phone number will be eliminated from this contact log. If she chooses to be contacted for future studies, her name and phone number will remain in the contact log. Participants’ contact information will be kept until after participants decide to stop active participation or 5-7 years after the study is completed.

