We will now work on implementing the intervention and assessing changes across interventions with regard to Aims 1-3 outcomes (screening, psychosocial facilitators, network effects). We plan on recruiting 150 Latina women to participate in the Intervention. 75 women will be recruited at The Resurrection Project and 75 women will be recruited from Centro Comunitario Juan Diego. No contact information on women who have participated in any previous focus groups or will we re-contact any woman who has already participated in a focus group for future trial. We will only invite new recruits for the intervention. We will be conducting educational classes and workshops at the two participating sites. The Intervention is broken down into 3 sessions at each site across 3 consecutive weeks. Each session will be held with 5-8 recruited participants. We will hold 5 – 9 sessions at each participating site for three consecutive weeks until we reach our target population of 150 Latina women. The variations in the implementation of Phase 3 Intervention will be the Workshops at each site. Besides each site conducting a Breast Cancer Education session at Session 1, TRP will conduct Communication and Volunteerism workshops at Session 1 and 2. Juan Diego will conduct Diet and Physical Activity workshops at Session 1 and 2. Our outcomes will be measured by Surveys assessed during Session 1, Session 3, and six months post-participation in workshops for 20-30 minutes. For participants were in Cohort 1 (who completed participation before approved consent addendum), they will be contacted by phone up to 3 times with a script including consent addendum information to be given that information, wherein they can elect to be notified about future studies, if they are interested. If they are not interested, their data will be eliminated from this file. For cohorts 2-15, after the participant completes the final/third survey, her data will be eliminated from this file, if she chooses not to be contacted for future studies. If she chooses to be contacted for future studies, her name and phone number (nothing else) will be kept and it will be recorded that she has completed participation, but is willing to be contacted in the future. Subsequently, each time she is contacted, this file will be updated to include a summary of the call. During each call, UIC staff will query the woman about her interest in being contacted in the

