future. If she chooses not to be contacted from future studies, her name and phone number will be eliminated from this contact log. If she chooses to be contacted for future studies, her name and phone number will remain in the contact log. Scripts for these calls will be submitted in future amendments/for other protocols focused on these future studies. Participants' contact information will be kept until after participants decide to stop active participation or 5-7 years after the study is completed. For participants who are still participating in June 2018 or who are enrolled after June 2018, mailed letters will be sent to participants who have non-working telephone numbers and/or for women who are non-responsive to 5 attempted phone calls. At the point when thank you cards are sent, the PI and UIC study team will note participants as "lost to follow up", which will indicate that no further contact should be made. If the participant responds/contacts the PI and study team and indicates they wish to continue to participate, the study team will change this status to "returned to study" and begin contact once again, based on participant preferences. If they do not contact the PI, they will remain "lost to follow up" and no contact will be made. To note, none of UIC-based study staff will access to the mailing addresses of participants. Rather, the letter will be included in a stamped envelope that will be provided to community partners (Centro Comunitario Juan Diego, The Resurrection Project). Community partners regularly engage clientele of their organization through letters as well as phone calls, including women who they have recruited to participate in this study. We will give stamped envelopes with the UIC IRB-approved letter to community partners, who will print address labels and mail letters to participants. To note, no UIC-based staff will have access to these addresses and community partners will only mail letters to participants who have already previously provided their addresses for regular correspondence with Centro Comunitario Juan Diego and The Resurrection Project. Agencies are the primary recruitment sites and agency staff are study staff listed in Appendix P. We are now requesting a waiver of consent and alteration of consent to provide the agency with a list of names of participants for whom letters will be mailed, as 1) the waiver would not adversely affect the rights and welfare of subjects; and, 2) the only way for study staff to reach these subjects is through transfer of this information to the agency staff. Subjects will contact the PI directly if interested. We also now include a recruitment script for women who are interested and contact the PI and study staff. The PI and UIC staff will then update contact information in study records. The PI will only know how many subjects have been mailed 1 letter. The PI and UIC staff will not know how many are returned/are undeliverable/have left the community based organization altogether. Only one mailed letter will be sent for each participant who cannot be reached. At the point when thank you cards are sent, the PI and UIC study team will note participants as "lost to follow up", which will indicate that no further contact should be made. If the participant responds/contacts the PI and study team and indicates they wish to continue to participate, the study team will change this status to "returned to study" and begin contact once again, based on participant preferences. If they do not contact the PI, they will remain "lost to follow up" and no contact will be made. Subjects who are interested will contact the PI or study staff at TRP and CCJD. TRP and CCJD staff [only staff in research study – i.e., listed in Appendix P] will refer the participants to UIC staff, who will have a list of the interactions requested for each individual participant. This list will be a password-protected file that is kept in a password-protected computer in a locked office at UIC (R:drive). To note, only study staff who are listed in Appendix P/have human subjects training will respond and engage participants who call the study site to optimize patient confidentiality. If the participant contacts the study team at these sites or at UIC and indicates they wish to withdraw/not be contacted by the PI, the study team at these sites will inform participants that no further attempted contact will be made for this study.

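### Do the file-deletion rules lose the Aim 3 peer-referral counts, and does the site-staff-recruited sensitivity analysis lack a usable definition?

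*Combined protocol and SAP*

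**What the plan says.** Aim 3 (section 3.0) predicts that empowerment women will refer more peers than education women. Section 6.2, Phase 3, treats coupon use as a behavioural measure of this, counted as women who take recruitment materials and people who then call. Women may recruit up to the third survey (sections 5.1, 6.1 and 6.2).

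Section 11.0 describes the files. The first is identifiable and holds the ID code, the coupon numbers and "the number of individuals who have called with the coupon numbers assigned to them". Its retention rule is "This information will only be kept across the months in which the participant is enrolled in the study". For Cohort 1, whose members are telephoned about later contact, "If they are not interested, their data will be eliminated from this file". For cohorts 2 to 15 the same happens after Survey 3 to women who decline. For a woman who accepts, section 11.0 says "If she chooses to be contacted for future studies, her information will be kept", whereas section 6.4 says "her name and phone number (nothing else) will be kept" and section 6.2 carries the same restriction. Sections 6.2 and 6.4 go on to speak of a contact log: for a woman who later declines, "her name and phone number will be eliminated from this contact log". Of the coded file, section 11.0 says "The second file will include the participant identification code and survey data".

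Section 9.0, Phase 3, adds a sensitivity analysis of the screening outcome in women recruited by staff of the study sites. It does not say how they are identified.

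**The concern.** Read one sentence at a time, the plan stores an outcome in a file that it then empties. The coded file is described as ID and survey data, and the survey topics in section 6.2 include no referral count, so nothing on the page moves the counts to where the analysis would find them. If the name-and-telephone restriction governs the whole identifiable file, no counts remain there after Survey 3. If section 11.0 governs, counts remain only for women who agree to later contact. That choice is made after the intervention, and the arms differ in their outreach and volunteering content, so the missingness could be related to arm. Multiple imputation is not a natural remedy for data deleted by design.

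The staff-recruited subset looks equally loose. No recruitment-source item is listed in the surveys or in either file. The sites are said in one place to take no part in recruitment, in another to help with it, in another to be the main recruitment venues, and in the Phase 6 background to have recruited the participants.

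**Working it through.** **The plan's own figure.** For network outcomes section 9.0 states f² = 0.05 with 150 women, two-sided 5% and 80% power. The normal approximation is f² = (z₀.₉₇₅ + z₀.₈₀)²/N = (1.960 + 0.842)²/150 = 7.85/150 = 0.052. The noncentral F gives 0.053. Both agree with the stated value to rounding.

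**What loss would cost, if it happened.** The documents give no share of women who accept later contact, so the shares here are assumptions. By the noncentral F, the detectable f² for the referral outcome would be:

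| Counts retained | Women | Detectable f² |
|---|---|---|
| 100% | 150 | 0.053 |
| 90% | 135 | 0.059 |
| 75% | 112 | 0.071 |
| 50% | 75 | 0.107 |
| 25% | 38 | 0.218 |

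So loss would matter. The question is whether the plan implies it.

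**Does it? The passages side by side.**

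1. *What is deleted.* Removal is from one named file. Nothing says the counts leave the study.
2. *When.* For cohorts 2 to 15, removal follows Survey 3. Referral is allowed until Survey 3. The count is therefore final when removal falls due, and no deletion rule cuts it short. Cohort 1 is described as having completed participation before the consent addendum, so its referral window had also closed by the time of the call.
3. *Is there a key?* The first file holds the participant ID, and so does the coded file. Sections 5.1 and 6.1 also have staff record coupon numbers against the participant ID, so the count can be merged without names. This holds even though another paragraph of section 11.0 says that names are kept apart from ID codes.
4. *Is there a duty to use it?* Section 6.2 says these counts will be measured as an Aim 3 outcome, and referrers must be identified to be paid.
5. *The name-and-telephone restriction.* Sections 6.2 and 6.4 introduce it in the setting of later contact and then call the record a contact log. It is reasonable to read it as limiting what stays on file for recontact, which removes most of the conflict with section 11.0.
6. *Women without Survey 3.* Section 5.0 expects 240 to enrol and 150 to complete, so 90 (90/240 = 37.5%) may not. That figure is general attrition and does not measure lost counts. The post-Survey-3 rule does not reach a woman who has no Survey 3, and her count can be taken at last contact.

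**The staff-recruited subset.** In section 6.2, Phase 3, the sentence excluding the sites from recruitment follows one saying that they distribute flyers and listserv messages to recruit women. It excludes peers as well, although peers recruit by coupon. Recruitment in that sentence must therefore mean handling contacts, screening and consent. Section 10.0 fits this: the sites help recruit but do not screen or take consent. These passages and the description of the sites as the main venues are then compatible. Only the Phase 6 background, which credits the partners with all participants, is loose. The sensible contrast is women reached through site outreach against women reached through a peer.

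**The case for a change.** The strongest case for a change is that deletion cannot be undone. A count removed without a copy may be unrecoverable, and the fallback is weak: the Call Log serves to pay referrers, and section 7.1 keeps it unlinked from questionnaires. Referral is a named part of an aim's hypothesis, and one sentence would settle the matter.

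Part of this stands. The transfer is not written. Sections 11.0, 6.2 and 6.4 do differ on what is kept. Two paragraphs of section 11.0 differ on whether names and ID codes share a file. No recruitment-source field is listed, and a coupon code alone would not supply one, because it is not tied to the caller's own study ID and a peer may pass on contact details without a coupon.

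The inference to planned loss does not stand. An unwritten export step differs from an instruction to discard, and that recontact choices differ by arm is conjecture. Requiring a source field also has a cost. It would need new collection unless the survey forms, which are not in the documents, already ask. Coding a woman as peer-recruited under her study ID would record that a referred caller took part, which the safeguards in sections 5.1 and 6.2 are written to avoid.

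**Conclusion.** No change to the plan follows. The missing transfer is a detail that a competent data manager supplies: the count is final when removal falls due, it can be merged by participant ID, and the plan commits to analysing it. The differing retention statements are drafting inconsistencies about a contact record, and the description of the sites' role is loose in one background sentence.

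The reach is small: one component of Aim 3 and one sensitivity analysis of the screening outcome. The primary screening analysis, social connectedness, network size, the sample size of 150 and the stated detectable effects are untouched. This rests on two assumptions: that the counts are taken before a row is removed, and that site-staff recruitment is read as outreach by the sites. If recruitment source was never recorded, the staff-recruited analysis would have to be reported as not done, and the main comparison would not change.

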Breach of confidentiality is the only other risk to individuals. Breach of confidentiality could entail divulging that individuals contacted staff to be screened and completed informed consent forms. The risk of divulging this confidential information is minimal and the potential for identity theft is limited by the way this data will be handled, given the encryption, password protection, and secure, locked office where the Call Log, electronic copies of informed consent forms and de-identified data will be stored and analyzed. De-identified data, including questionnaires, transcripts, individual-level Phase 5 observation documents (e.g., Participant Encounter Logs), and Phase 6 community volunteerism data, will not be linked in any way to any individual participants' contact information, which minimizes the possibility of identifying individuals or stealing personal information. Specifically, Call Logs will only be linked to electronic copies of signed informed consent forms – both of which will be kept in password-protected computers in locked offices. Neither of these will be linked to questionnaires, individual-level Phase 5 observation documents, and Phase 6 data, which will only be marked by a 6-digit identification code that has no relationship to participants' information, nor to transcripts, which will undergo a process such that no record of conversations during interventions will have personal identifying information. There is no possibility of conducting this investigation without the data being used.

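### Does the confidentiality wording remove the name-to-code link that the repeated surveys and referral counts need?

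*Combined protocol and SAP*

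**What the plan says.** Section 11.0 describes two master files. Of the first it says: "The first will include identifiable elements, the participant identification code, the dates in which women have been contacted/interacted with staff". That file also holds coupon numbers and "the number of individuals who have called with the coupon numbers assigned to them". The second file carries the same participant code with the survey data and no identifiers. The shared code joins a named woman to her questionnaires.

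Later in 11.0, the text says that "their names and contact information will be kept in a separate file that has no connection to the identification codes used in questionnaires". Section 7.1 says of the Call Logs and signed consent forms: "Neither of these will be linked to questionnaires". The same paragraph of 7.1 goes further and denies any linkage at all between de-identified data and contact information. Section 13.2 is milder and rules out only a direct link between study data and names.

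On retention, for cohorts 2 to 15, a woman who declines future contact has her row removed after the third survey in 6.2, 6.4 and 11.0 alike. For a woman who accepts, 11.0 says "her information will be kept and it will be recorded that she has completed participation". Section 6.2 says "her information name and phone number (nothing else) will be kept" and 6.4 says "her name and phone number (nothing else) will be kept". Section 11.0 also says, just before this, that the first file's content is held only for the months of enrolment. Sections 6.2 and 6.4 add a limit of 5 to 7 years for contact details, and 6.3 and 13.1 call for destruction of electronic materials after the trial.

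**The concern.** Several planned steps need a link between a woman and her code. The psychosocial analysis in 9.0 is a two-level model of repeated surveys within participants, so Survey 3 must be matched to Surveys 1 and 2. It is taken six months after Session 3, when the coded workbooks have already been collected. Coupons are logged against the participant code (5.1 and 6.2), and the number of callers per woman is an Aim 3 measure. Phase 6b plans to link partner-held volunteering records, which 7.1 says carry only the six-digit code.

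If staff took the denials in 11.0 and 7.1 at face value, no such key would exist and these joins would fail. If they applied the stricter retention rule without first copying the referral counts, those counts could be lost for good. Staff also have two texts on what to keep for the same woman. The stakes would be repeated-measures data that cannot be assembled, and an Aim 3 outcome with avoidable gaps.

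**Working it through.** The plan gives no figure for this point, so the check sets the texts side by side. The only arithmetic is counting.

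**1. Is the link denied?**
- 11.0, sentence on names and contact details: yes, in conflict with the two-file description in the same section.
- 7.1, sentence on Call Logs and consent forms: not by itself, because those are different documents from the first master file. The broader denial in the same paragraph does conflict.
- 13.2: no. A coded two-file scheme meets a bar on direct links.

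Two sections therefore conflict with the scheme and one does not. The two-file description is the only operational account of how data are coded, and 5.1, 6.2 and 9.0 all presuppose it. The denials sit in general assurances about confidentiality.

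**2. Can the three surveys be joined?**
- Planned surveys: 150 women x 3 = 450, matching the count in 9.0. Of these, 150 x 2 = 300 are Surveys 1 and 2, and 150 are Survey 3.
- Deletion point for cohorts 2 to 15: after the third survey, in 6.2, 6.4 and 11.0.
- Cohort 1: women "who completed participation before approved consent addendum", so their surveys were finished before the re-contact question arose.
- Planned surveys that a stated rule would cut off from the key before completion: 0 of 450.

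**3. What differs after Survey 3?** The first file has five kinds of content: identifiers, code, contact dates, coupon numbers and caller counts.
- Declines re-contact: removed under every version, so no difference.
- Accepts re-contact, under 6.2 and 6.4: name and phone number stay; the other four kinds go.
- Accepts re-contact, under 11.0: no fields are listed. On the widest reading all five kinds stay. Read with the enrolment-only sentence and the more specific 6.2 and 6.4, only name and phone stay.

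The disagreement thus ranges from none to four of the five kinds of content, and it concerns only accepters in cohorts 2 to 15.

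**4. What would the narrow rule remove that an analysis needs?**
- Aim 3 counts: 6.2 commits staff to measuring them. Women may refer others until the third survey, and deletion comes after it. Counting at that point and storing the result under the code is not forbidden anywhere.
- Phase 6b: the main measures are numbers of activities, of women interested and of women attending, which need no survey join. The secondary predictor regressions would need one if their predictors come from the surveys. The plan gives no timing for Phase 6b relative to Survey 3, and 12.1 calls Phase 6 a pilot.

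**The case for a change.** The strongest reply is that these are assurances in a protocol under ethics review and the trial's own procedures contradict them. Staff should not have to guess which text governs deletion, because deletion cannot be undone. Phase 6b gives the point substance: if only name and phone number survive, a woman past Survey 3 can be called and can consent, but her partner records cannot then be matched to her surveys.

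Most of this stands as a description of the text. The sentences in 11.0 and 7.1 are wrong as written, the retained fields for accepters are unclear, and the 5-to-7-year and destruction rules add further loose ends. What does not follow is that the plan cannot be carried out. The two-file scheme is explicit and workable, and the key lasts as long as the repeated surveys need it. The caller counts are a committed measure that any data manager would transfer before clearing a row. The Phase 6b difficulty depends on timing the plan does not give and touches only secondary regressions.

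Two neighbouring matters do not strengthen the case. The subset recruited by site staff, used in a 9.0 sensitivity analysis, is an undefined term about recruitment source. Modelling referral chains is limited by what 5.1 and 6.2 allow to be stored from a peer's call. Neither turns on the wording about names and codes.

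**Conclusion.** The concern identifies a true inconsistency in the confidentiality and retention text, but it does not call for a change to the plan. It is a drafting fault together with a data-handling gap that staff fill sensibly. Its effect on sample size, power, the primary regression, the survey-based network outcomes and the joining of the three surveys is nil. The possible loss is confined to women in cohorts 2 to 15 who accept re-contact and whose Phase 6b records are obtained after Survey 3. It would reach only secondary analyses of a pilot. No share of women can be put on it, because the documents give neither re-contact acceptance rates nor the timing of Phase 6b.

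This rests on two assumptions: that staff follow the two-file description in 11.0, which the other procedures require, and that referral counts are recorded under the participant code before a row is cleared. Rewording would make the document more accurate, but no result is shown to depend on it.
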